Smart Choices 4 Teens required that parents and teens complete the activities online separately. Following completion of the component, teens and parents discussed scenarios reflecting teen choices regarding alcohol use and relationships as an offline activity. Families had to indicate that they had completed the discussion to move on to the next component. In addition, as the program is family based, families could only progress to the next component if their other participating family member had also completed that component. For example, if a teen had completed the Communication component, but their parent had not, the teen would not be able to begin the Alcohol component until their parent had also completed the Communication component. On average, the Communication component took families 20.29 min to complete (21.83 minutes for parents, 18.75 minutes for teens). The Alcohol component took 15.94 min (16.34 minutes for parents, 15.53 minutes for teens), and the Relationship component took 19.75 min (19.79 minutes for parents, 19.71 minutes for teens). The amount of time spent in family discussions of the scenarios is not included in these averages.

**Description of the Control Condition:** Families in both the control and intervention condition received links to resources, including hotline numbers and websites to provide information about teen alcohol and drug use, sexual behavior, suicide, and other health issues. The websites provided contact information for crises, as well as information about the specific health issue (e.g., the Mothers Against Drunk Driving website provided information about rates and consequences of impaired driving). All families also had access to an 800 number throughout the duration of the project to contact with the research team.

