*Survey and Randomization Procedures:* Separate surveys were conducted for parents and teens at baseline (at time of enrollment), and at 6, 12 and 18 months later. After both parent and teen completed the baseline survey, families were randomly assigned to either the intervention or control condition using a computer-generated program. Automated e-mails and texts were sent to invite families to complete the follow-up surveys. One week after follow-up survey invitations were sent, reminder e-mails and texts were sent to families who had not completed the surveys, with the e-mails/texts repeated after another week of nonresponse. One week later, separate phone calls were made to parents and teens if they had still not completed. Participants could complete the surveys up to 2 months after surveys were initiated. Of the 411 enrolled dyads, 315 teens (76.6%) and 364 parents (88.6%) completed the 6-month follow-up surveys, and 311 teens (75.7%) and 354 parents (86.1%) completed the 12-month follow-up surveys and 309 teens (75.2%) and 357 parents (86.9%) completed the 18-month follow-up surveys.

*Measures:* Measurement of assignment to condition (experimental vs. control) was based upon the original randomized assignment. Program dosage (no exposure, exposure to alcohol component, exposure to relationship component) was based upon tracking progress through the program, automated in the online delivery.

*Teen alcohol use.* Alcohol items were adapted from the National Longitudinal Study of Adolescent Health (Harris et al., 2008) and asked in surveys. Teens first reported whether they had consumed alcohol over the past 6 months and past 30 days (1 = Yes, 0 = No).

*Quantity and frequency of alcohol use.* Teens reported their frequency of drinking over the past 30 days and past 6 months (0 = Never, 1 = once a month, 2 = 2–3 times a month, 3 = once a week, 4 = 2–3 times a week, and 5 = daily or almost daily). The variable was recoded to more closely approximate the actual number of times used over the time period. For example, 2–3 times a month in the last 30 days was recoded to 2.5, whereas 2–3 times a month over the past 6 months was recoded to 15 (2.5 = 6 months). Teens also reported the usual amount they drank on drinking days (0 = less than one to 7 = more than six).

*Drunkenness:* To assess drunkenness, teens reported the number of times they had gotten “drunk or very, very high” on alcohol over the time period (e.g., past 6 months, past 30 days).

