*Communication regarding teen alcohol use.* Both parents and teens responded to items regarding their alcohol communication at each time period (baseline, 6 months, 12 months). All parent–teen alcohol communication items were adapted from Turrise, Mastroleo, Mallett, Larimer, and Kilmer (2007)(Turrise et al., 2007) and Reimuller, Hussong, and Ennett (2011)(Reimuller et al., 2011). Three constructs were assessed: (a) Consequences and

Expectations: alcohol communication regarding consequences and parental expectations about teen alcohol use (12 items, e.g., how drinking could get the teen in trouble with a parent or the law; drunk driving consequences), 1 = never to 5 = very often. Items were averaged to create separate parent and teen scales (parent report:  $\alpha = .95$  at baseline,  $.97$  at 6 months,  $.97$  at 12 months; teen report:  $\alpha = .96$  at baseline,  $.96$  at 6 months, and  $.97$  at 12 months). (b) Safe drinking strategies: two items that consisted of teen drinking was acceptable in moderation, and teen drinking was acceptable under supervision, 1 = never to 5 = very often. Items were averaged to create separate parent and teen scales at each time point (parent report:  $r = .72$ ,  $p = .001$  at baseline,  $r = .72$ ,  $p = .001$  at 6 months,  $.74$ ,  $p = .001$ . at 12 months; teen report:  $r = .73$ ,  $p = .001$  at baseline,  $r = .72$ ,  $p = .001$  at 6 months, and  $r = .78$ ,  $p = .001$  at 12 months); and (c) Both parents and teens responded to one question as to how often parents had discussed social host laws with them (1 = never to 5 = very often).

*Overall frequency of communication about sex:* The overall frequency of sex communication was assessed with a single item adapted from the evaluation of the program Parent Handbook for Talking with College Students about Alcohol (Turrissi et al., 2010) — “Overall, how often have you talked to your parent about sex”—with response options ranging from (1) never through (5) very often.

*Topics of conversation about sex:* Adolescents were asked to report whether their parents had talked about specific topics with them, adapted from the evaluation of Family Matters (Reimuller et al., 2011).

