### Sample Characteristics:

Among enrolled families at baseline, parents were on average 43.7 years of age ( $SD = 6.7$ ) and their teens were 16 or 17 years of age ( $M = 16.4$ ,  $SD = 0.5$ ). Mothers comprised 84.7% of the parents and slightly more than half (55.3%) of the teens were females. Household size ranged from two to 12 ( $M = 4.5$ ,  $SD = 1.6$ ). About one-tenth (9.5%) of the teens were Hispanic/Latino.

Teens reported the following race/ethnicities: 72.5% White, 1.9% Asian, 11.7% African American, 1.0% Native American, 8.3% Multiracial, 2.7% some other race, and 1.9% unreported. No significant differences were found between the experimental and control conditions on demographic characteristics at baseline.

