### **Analyses:**

Descriptive analyses were conducted first to describe rates and mean scores of outcomes overall and by condition across three assessments to check the randomization.

Selection model: Because families chose how much of the intervention to which they were exposed, we conducted a probit analysis predicting whether or not a family completed the alcohol or relationship component from baseline measures. Based on this analysis, an instrumental variable, inverse Mills’ ratio (IMR) representing the underlying selection processes was included as a covariate in our primary dosage analyses (Heckman, 1979). The IMR (non-selection hazard) was calculated in Stata using the two-step procedure described in Heckman (1979). When the IMR is significant in a model, this indicates that the predicted probability of completing the component is associated with the outcome. That is, the same factors that predispose families to complete (or not complete) the component are related to the outcomes. In models where dosage is significant, this indicates that even accounting for factors that are related to completing the program, that dosage is still related to outcomes.

Conducting analyses in SPSS 21, dichotomous outcomes were examined using multiple logistic regression, while continuous outcomes were examined using multiple linear regression. Listwise deletion was used for missing cases. For all regression analyses, the baseline value of the outcome variable, teen gender, teen age, and teen ethnicity, an inverse Mills’ ratio and intervention condition, were covariates to determine whether dosage predicted the outcome for a specific follow-up period (i.e., 6, 12 18 months).

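### The outcome models name only teen demographics and the selection model's predictors are unlisted, so control of parent-side selection into dose is not shown; adding the other informant's baseline would guard the alcohol-communication results

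*Combined protocol and SAP*

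**What the plan says.** All references are to the combined protocol and SAP.

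- **Outcome models (Analyses).** One list serves all regressions: "the baseline value of the outcome variable, teen gender, teen age, and teen ethnicity". The sentence continues with the IMR, "ratio and intervention condition, were covariates to determine whether dosage predicted the outcome for a specific follow-up period". The further adjusters mentioned in Assessment of Efficacy are again characteristics of the adolescent.
- **Selection model (Analyses).** A probit is fitted, "predicting whether or not a family completed the alcohol or relationship component from baseline measures". The resulting IMR, "representing the underlying selection processes was included as a covariate in our primary dosage analyses", is the plan's device for selection. The probit's predictors are not listed.
- **How a dose is reached (Description of the Intervention).** "families could only progress to the next component if their other participating family member had also completed that component". Under Exposure to Treatment, the plan itself gives parents' values as one reason families are hard to engage.
- **What was collected from parents.** Survey and Randomization Procedures: "After both parent and teen completed the baseline survey, families were randomly assigned". Measures, on the multi-item alcohol-communication scales: "Items were averaged to create separate parent and teen scales". Both informants also answered the social host law item. Sample Characteristics gives parent age and parent gender: "Mothers comprised 84.7% of the parents".

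**The concern.** The main question is whether dose predicts outcome, and dose was chosen by families. Completing a component depended on the parent as much as on the teen. Parents who already talked more about alcohol at baseline may have been more likely to finish, and they may also score higher at follow-up whatever the program did. If nothing in the model carries that difference, it is read as a dosage effect.

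The outcome models contain no parent term in the teen-report analyses, and only the parent's own baseline in the parent-report analyses. Whether the IMR fills the gap depends on a predictor list that the reader cannot see. The efficacy text nevertheless says that selection bias was controlled and singles out social host law conversations. For that outcome, the only baseline control named is one item from one informant, although the other informant answered the same item before randomisation.

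**Working it through.** The plan states no figure on this point, and no correlations, R² values or probit coefficients. The sizes below are therefore ranges under stated assumptions.

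**Inputs from the documents**
- 411 dyads; 76.6% of teens responded at 6 months.
- Completion in the intervention arm was 49.5% (Alcohol) and 42.7% (Relationship). Among arm sizes from 195 to 216, only 206 fits both: 102/206 and 88/206.
- Alcohol completers with 6-month teen data: 102 × 0.766 ≈ 78. Non-completers: 104 × 0.766 ≈ 80. Equal response in the two groups is assumed.

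**Assumed inputs (SD units)**
- Outcome with own baseline: r1 = 0.5.
- Outcome with the other informant's baseline: r2 = 0.3 to 0.4.
- Parent and teen baselines with each other: ρ = 0.2 to 0.4.
- Completers higher by d1 = 0.1 on own baseline and by d2 = 0.2 to 0.4 on the other informant's.

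**Step 1. Bias if the other informant's baseline is in neither model**

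Bias = [(r2 − r1ρ)/(1 − ρ²)] × (d2 − ρd1).
- Low end (r2 = 0.3, ρ = 0.4, d2 = 0.2): (0.10/0.84) × 0.16 = 0.019 SD.
- High end (r2 = 0.4, ρ = 0.2, d2 = 0.4): (0.30/0.96) × 0.38 = 0.119 SD.

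Standard error of the completer versus non-completer contrast: √[0.75 × (1/78 + 1/80)] = 0.138 SD. With two-sided rejection at 1.96 (the documents state no alpha), a nominal 5% false-positive rate becomes 5.2% at the low end and 13.8% at the high end.

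**Step 2. The same bias under the planned model with the IMR**

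The formula in step 1 contains no IMR, so the planned model was simulated with no true dosage effect.
- r2 = 0.4, ρ = 0.2, completer gaps of about 0.38 and 0.12 SD: bias about 0.11 SD when the measure is left out of the probit, and below 0.01 SD when it is in.
- r2 = 0.3, ρ = 0.4: bias about 0.02 to 0.03 SD when left out, and below 0.01 SD when in.

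A separate large-sample simulation used one parent factor, with outcome slopes of 0.1 to 0.3 and probit slopes of 0.1 to 0.5. It gave 0.01 to 0.21 residual SD when the factor was left out, and within 0.01 of zero when it was in the probit or adjusted for directly.

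**Step 3. Other informant's baseline added to the outcome model**

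Simulated with n = 315 and the IMR included, the bias went to about zero whether or not the measure was also in the probit. The dosage standard error fell from 0.141 to 0.132–0.133 at best and was unchanged at worst.

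**Step 4. Precision by formula**

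R² with both baselines = (r1² + r2² − 2r1r2ρ)/(1 − ρ²), against r1² = 0.25 alone.
- Low end: (0.25 + 0.09 − 0.12)/0.84 = 0.262. Residual variance falls by 0.012/0.75 = 1.6%, and the standard error by 0.8%.
- High end: (0.25 + 0.16 − 0.08)/0.96 = 0.344. Residual variance falls by 0.094/0.75 = 12.5%, and the standard error by 6.5%.
- At r2 = 0.25 the fall in standard error is only 0.2 to 1.6%.

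These figures ignore any association of the added covariate with dose. Allowing for it, the standard error ratio is √[(1 − R²outcome)/(1 − R²dose)]. With 5% of outcome variance explained, it is 0.975 if the covariate is unrelated to dose, 1.00 if it explains 5% of dose, and 1.03 if it explains 10%.

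**The case against.** The strongest reply is that the plan already has a device for selection. The probit models completion by the family, its predictors are not limited to teen items, and a parent baseline survey was in hand. If parent communication was among the predictors, step 2 leaves almost nothing to correct. That stands, and it means a bias cannot be asserted. It does not show that the bias is absent, because the list is not given.

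Several stronger readings are tempting, and the documents do not support them:
- *That every covariate is the teen's.* The IMR and condition belong to the family, and in parent-report models the baseline value is the parent's.
- *That parent measures went unused.* They may have entered through the probit.
- *That the estimates are materially less precise.* The gain is small. It can vanish or reverse if a covariate predicts completion better than outcome. In the logistic models, adjustment does not in general shrink the standard error of the log odds ratio.
- *That the cross-informant argument covers dating rules and sex communication.* Measures describes those as adolescent reports, with no parent counterpart. Only parent age and gender could be added, and their prognostic value is unknown.

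A technical objection also stands in part. If every probit predictor also enters the outcome model, the IMR is identified by functional form alone, and the plan states no exclusion restriction.

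The predominance of mothers is openly reported and is a matter of generalisability. A mother-only estimate would use about 85% of the dyads and would probably differ little from the overall one.

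**Conclusion.** The point holds as a gap in demonstrated control, with a cheap safeguard available. No parent characteristic is named in the outcome models beyond the own-baseline score in parent-report analyses. The unlisted probit predictors mean that the documents do not show parent-side selection into dose to be controlled. For the alcohol-communication outcomes, the possible false dosage effect is roughly 0.02 to 0.12 SD if parent measures are absent from the probit, against a standard error of about 0.14 SD, and about zero if they are present. These figures rest on assumed correlations and completer differences, and on equal response among completers and non-completers.

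A reader might infer that the reported dosage effects are biased. The documents do not support that, since they leave open which probit was fitted. The precision gain of about 0 to 6% in the standard error is a secondary benefit and would not justify the change by itself.

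**What to change.** In Analyses, add the other informant's baseline score on the same construct to each alcohol-communication model: the parent's baseline in teen-report models and the teen's in parent-report models. Keep the rest of the covariate list. The adjustment works whether or not the measure was in the probit.

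List the probit predictors and confirm that at least one stays out of the outcome model, so that the IMR does not rest on functional form alone.

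Parent gender and parent age may be added as a sensitivity analysis in the communication and dating-rule models. A mother-only estimate is optional.

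The cost is one to three degrees of freedom per model, a re-run of existing models, and a few cases lost to listwise deletion on the added baseline items. No new data are needed, because both baseline surveys were completed before randomisation.

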## II. Purpose of Study

Smart Choices 4 Teens was created by adapting materials from two evidence-based prevention programs that are both booklet-based and independently completed by families: Family Matters (Bauman et al., 2001) (designed for parents of younger adolescents) and A Parent Handbook for Talking with College Students about Alcohol (Abar & Turrisi, 2008; Turrisi et al., 2001) (designed for parents to prepare their adolescents for the first year as college students). The intent was to determine whether this online program would improve the teen’s ability to make safe and responsible choices regarding their alcohol use and sexual behaviors as compared to teens not exposed to the program.

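### The alcohol regressions described test self-chosen dosage, so the alcohol efficacy claim rests on no randomised comparison set out in the document

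*Combined protocol and SAP*

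**What the plan says.** The Survey and Randomization Procedures paragraph has families randomised after both baseline surveys, and Measures records condition as originally assigned. II. Purpose of Study sets the question as whether teens make safer choices "as compared to teens not exposed to the program".

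The Analyses section then describes three things:

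- **Descriptive analysis.** This covers "rates and mean scores of outcomes overall and by condition across three assessments to check the randomization".
- **Selection model.** Because families chose their own exposure, a probit was fitted "predicting whether or not a family completed the alcohol or relationship component from baseline measures". An inverse Mills' ratio (IMR) from it "was included as a covariate in our primary dosage analyses". A significant IMR is taken to mean that "the predicted probability of completing the component is associated with the outcome".
- **Outcome regressions.** These are logistic or linear. In all of them the baseline outcome, teen gender, age, ethnicity, an IMR and "intervention condition, were covariates to determine whether dosage predicted the outcome for a specific follow-up period". On missing data: "Listwise deletion was used for missing cases".

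The Assessment of Efficacy-Overview claims efficacy against teen alcohol use. It ties better results to more exposure, cites dosage findings on several alcohol indicators, and says baseline rates and selection bias were controlled. It mentions a main effect of the intervention only for frequency of communication about sex and for dating rules.

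**The concern.** Randomisation protects the comparison of families as assigned. It does not protect a comparison of families that finished the program with families that did not. If an unmeasured family characteristic affects both completion and later drinking, the dosage term can be significant with no program effect, or can hide a real one.

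With 49.5% of intervention families completing the alcohol component (Exposure to Treatment), dosage and assignment are very different exposures. A reader is told that the program is efficacious for alcohol use on the unprotected comparison, while the protected one is not described. The point is confined to teen alcohol use, quantity and frequency, and drunkenness.

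**Working it through.** **Inputs from the document.** 411 families enrolled; 315, 311 and 309 teens followed at 6, 12 and 18 months; 49.5% completion of the alcohol component; the covariates listed under Analyses. The retention percentages reproduce: 315/411 = 76.6%, 311/411 = 75.7%, 309/411 = 75.2%. Missing teens therefore run from 23.4% to 24.8%.

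**Assumptions.** Control dosage is 0: Description of the Control Condition says "Families in both the control and intervention condition received links to resources" and gives controls no program access. Allocation is taken as 1:1, which the document does not state.

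**What the two terms estimate.** Take the linear model with completion as yes/no and leave the other covariates aside: mean outcome = a + c × condition + d × dosage.

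- Controls: a
- Intervention non-completers: a + c
- Intervention completers: a + c + d

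So d is completers minus non-completers within one arm, and c is non-completers minus controls. The randomised contrast is c + 0.495 × d, which the document does not report.

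A null simulation (311 teens, one unmeasured factor loading 0.5 on completion and −0.5 on outcome) illustrates this. The mean dosage coefficient was −0.395 and the mean condition coefficient +0.193, both wrong. Combined they give 0.193 + 0.495 × (−0.395) = −0.003, which matches the by-assignment estimate. Having condition in the model does not supply a randomised test.

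**What the IMR adds.** I read it as a single hazard computed from baseline measures and entered as a covariate. The document's own gloss in terms of predicted probability supports this reading, but no formula is given. In that form it adjusts for measured selection only.

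**How large the bias could be (illustrative, linear outcome).** The true effect is zero, with 411 families, 49.5% completing, 76.6% followed, the listed covariates and a single-hazard IMR, at 3,000 trials per setting. An unmeasured trait has loading 0.3 to 1.0 on completion and lowers follow-up drinking by 0.1 to 0.3 SD in total. The middle setting is 0.5 and 0.2.

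| Trait's effect on baseline drinking | Dosage bias (SD), range | False positives, range | Middle setting |
|---|---|---|---|
| None | −0.040 to −0.331 | 6.5% to 66.2% | −0.138, 16.0% |
| Half as strong | −0.034 to −0.243 | 6.4% to 41.4% | −0.102, 11.1% |
| Equally strong | −0.020 to −0.154 | 5.4% to 19.6% | −0.064, 7.6% |

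Reversing the selection reverses the sign (+0.023 to +0.158 SD in the last row's case). With no such trait the dosage test is close to valid (4.9% to 5.7%). Analysis by assignment rejects in 3.8% to 5.8% of trials throughout, if dropout does not differ by arm.

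**What analysis by assignment can detect.** With an SE of about 0.098 SD (1:1 allocation and a baseline to follow-up slope of 0.5, both assumed):

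- Effect by assignment for 80% power: (1.96 + 0.84) × 0.098 = 0.27 SD.
- In completers, if non-completers gain nothing: 0.27/0.495 = 0.55 SD.
- Power for a true completer effect of 0.3 SD: 0.3 × 0.495 = 0.1485; Φ(0.1485/0.098 − 1.96) = 33%.
- Power for 0.5 SD: 0.5 × 0.495 = 0.2475; Φ(0.2475/0.098 − 1.96) = 71%.

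**The case against.** **The document is a summary.** The relationship main effect comes from a model the Analyses section does not describe, and readers are sent to outside reports. An alcohol analysis by assignment may exist. This stands, and limits the point to what is described here. It does not change the fact that the overview names dosage as its alcohol evidence.

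**The Purpose speaks of exposure, not assignment.** On that reading the dosage model addresses the right question. But a question about exposure does not make completers and non-completers comparable. A protected estimate of the effect of exposure would use assignment as an instrument.

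**The plan addresses selection and is open about uptake.** True. A control-function form of the Heckman correction could also remove more of the bias: in simulation it rejected in 4.5% to 5.9% of null trials. There, joint normality and an excluded predictor held by construction, and its median SE was 0.44 to 0.66 against 0.14 for the single-hazard model. The document names no excluded predictor.

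**The simulated sizes depend on assumptions.** Also true. The 66% needs a trait that explains about 46% of latent completion variance (1.0/2.19) and leaves baseline drinking untouched. With an assumed baseline proxy correlated 0.5 with the trait, the middle-setting rates fall from 16% to 12% (no effect on baseline) and from 8% to 6% (equal effect). Dichotomising the outcome at an assumed 30% positive gives 11% and 6%. The figures show that the dosage test can mislead, not that it did.

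**Conclusion.** The point holds and needs correcting. As described, the alcohol efficacy claim of a randomised trial rests on a self-selected comparison, and no randomised alcohol comparison is set out. This follows from the model statement and the algebra, given zero control dosage, and needs no simulated value. The direction and size of any bias in this trial are unknown, because the document identifies no unmeasured factor. Under the stated assumptions the simulated bias runs from 0.02 to 0.33 SD, with about 0.06 to 0.14 SD at the middle settings. The claim to have controlled selection bias goes further than the analysis supports.

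**What to change.** 1. For every listed alcohol outcome at 6, 12 and 18 months, regress the outcome on assigned condition, its baseline value, gender, age and ethnicity, linear or logistic as now, without dosage or the IMR. Make this the main alcohol comparison and label it a re-analysis. If it already exists in the outside reports, state it here. Reporting all outcomes and times avoids choosing among them afterwards.
2. Say that listwise deletion makes it a complete-case comparison, and give teen follow-up by arm; only totals appear now.
3. Rest the alcohol efficacy wording on step 1. For example: By assigned condition, the effect on [outcome] at [month] was [estimate, 95% CI]. Families that completed more of the program had [better/worse/similar] outcomes after adjustment for baseline measures; this comparison is not randomised.
4. Keep the dosage models as secondary. Stating the probit predictors and IMR formula would help readers judge them. A complier-average estimate is optional.

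**Cost.** Re-analysis and rewording, with no new data if the analysis file still exists. If it does not, the overview can still be reworded as an association with exposure. The by-assignment effect is diluted to about half if non-completers gain nothing, will probably look less favourable, and has the limited power shown above for continuous outcomes. It is not immune to dropout: if follow-up depends on the unmeasured trait in one arm only (assumed logit slopes 0.5 to 1.0), it is off by 0.01 to 0.06 SD, with 5% to 8% false positives.
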